From each of these geographically-stratified study sites, 32 green intervention homes and 32 control homes (total = 64 homes * 13 study sites = 832 homes) will be included. Within each study site (i.e., city), both the green intervention and control homes will be from the same housing development or neighborhoods to ensure homogeneity with regard to housing type and other socioeconomic factors. Changes in environmental measurements (pesticides, VOCs, particulate matter (i.e., PM 2.5 and 1.0), indoor allergens, and fungi) over the 1-year follow-up in both types of housing (green intervention and control) will be compared, thus each home's follow-up measurements will be compared with its own baseline exposure level. This two-group pre-post within-group and between-group comparison will increase ability to detect differences in exposure levels and asthma outcomes that might result from the green renovations in our study. In addition, we will compare environmental measurements and health outcome data with national surveillance data (i.e., National Health and Nutrition Examination Survey (NHANES) and the National Lead and Allergen survey) or other relevant populations (e.g., National Cooperative Inner City Asthma Study (NCICAS), Inner City Asthma Study (ICAS)). At this time, these sites have not been determined by HUD and CDC. When the study sites are selected, the data collection partners will include: 1) CDC; 2) HUD, and 3) the contracted research institutions (to be determined).

An overview of the study implementation is described below. Briefly, study sites will be selected, participants will be recruited at each study site, survey, clinical, and environmental sample collection will occur at repeated time points, samples will be analyzed in selected laboratories, statistical analysis will be conducted, and results will be translated to participants and the community in general. All study consent forms and questionnaires will be available in both English and Spanish (by certified translators). Reading level will be maintained at an 8th grade level (Flesh-Kinkaid assessment available through Microsoft Word).

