Sample size overviews: The most complete data to obtain sample size estimates for our proposed study are derived primarily from studies of allergens and asthma. Based upon our calculations, we estimate that we will need at least 13 green buildings and 13 control buildings with at least 25 apartments in each building for a total $n = 650$ to detect differences in environmental exposures (notably allergens). In addition, we need at least 548 asthmatic children ($n=274$ in green and $n= 274$ in control buildings) to detect differences in asthma symptom days. With an anticipated loss to follow-up over a 1-year period = 20%, we will need at least 688 children with asthma (7-12 years) and 814 homes to assess exposure differences. We will enroll the children from 832 homes in order to ensure adequate power to detect both the asthma and exposure outcomes for the 13 study sites (i.e., 64 homes in each study site). The details of our sample size calculations are listed below and the equations that were used were from a book on longitudinal data analysis by Diggle, Liang, and Zeger (1994).

Sample size calculations for the overall difference between environmental exposures in green vs. control homes can be given as a simple test of two proportions and means; however a specific difficulty arises when trying to adjust for temporal and spatial correlations between measurements. A study that had enough measurements to assess spatial and temporal correlation was an integrated pest management (IPM) study conducted in New York

City (Chew et al. 2006; Kass et al. 2009). We have used the design effect from this study to estimate the number of clusters (or buildings) needed to detect differences in cockroach allergen because IPM is also one of the main green characteristics in the Green Housing Study. Assumptions from the aforementioned study comparing IPM to non-IPM homes are listed below:

- 1 13 buildings
 - 2 About half were treatment and the other half control
 - 3 3 repeated measures at: baseline (before IPM), 3months later (post-IPM), and 6months later (post-IPM)
 - 4 On average, 25 apartments within each building were measured
 - 5 For the control homes, the correlations between baseline and 3-month follow-up cockroach allergen measurements and 3-month and 6 months follow-up measurements were approximately equal to 0.5.
- Design effect due to clustering = 3.62

Equation 1. Sample size for repeated measures – cockroach allergen.

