$$m = D * [2(z_{\alpha} + z_{\rho})^2 \{1 + (n - 1)\rho\}] / (n\Delta^2)$$

m = number in each group (e.g., intervention and non-intervention)

n = number of repeated measurements (equals 3 in this scenario)

z_{α} = Z score for alpha = 0.05

z_{ρ} = Power, set at 0.80

ρ = correlation among repeated observations

$\Delta = d / \sigma$ where d is the smallest meaningful difference and σ is the standard deviation

D = Design effect due to clustering (This was not in the formula used by Diggle et al., but was added to adjust for clustering expected in our study)

Note: we also assumed a design effect (e.g., increase (multiplicative) sample needed because of the effects of clustering) equal to 3.62. This is the ratio in clustering sampling variance divided by the simple random variance (of the same size) (i.e., the denominator without clustering taken into account).

When calculating the sample sizes, we used two standardized effect sizes based on the IPM study: 0.37 and 0.30. The effect size of 0.37 is based on the ability to detect a difference of 0.8148 ln units of the *Blatella germanica* cockroach allergen (i.e., Bla g 2) and a standard deviation of ~ 2.2. The effect size of 0.30 is based on the ability to detect a difference of 0.649 ln units of Bla g 2 and a standard deviation of 2.2. We also assumed an alpha of 0.05 and a power of 80%). The sample size based on changing the expected correlation between repeated measures would result is presented in Table 8.

Assuming a correlation of 0.5 we get the following:

- 1 With assumption 1, we would need 16 buildings (8 green and 8 control) with at least 25 apartments per building
- 2 With assumption 2, we would need 26 buildings (13 green and 13 control) with at least 25 apartments per building.

Table 8. Sample size requirements for number of buildings.

Correlation between repeated measures	Sample size requirements (number of buildings)	
	Assuming Delta=0.377	Assuming Delta=0.30
0.2	6	9
0.3	7	11

0.4	8	12
0.5	8	13
0.6	9	15
0.7	10	16
0.8	11	17

*samples size is for each group (e.g., 8 buildings means 8 control and 8 green buildings)

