(based on Tuomainen et al, 2003)			
Piperonyl butoxide			
0.8 ng/m^3 decrease	3.6	0.33	418
(based on Williams et al, 2006)			

* $\alpha = 0.05$, $1-\beta = 0.80$

Summary of samples size for environmental exposures: Of the intervention studies relevant to green housing, the sample size calculations based upon the cockroach allergen intervention study provided the most information to inform our estimates of sample size required for the Green Housing Study. Because [name] was a co-author on the manuscript and had analyzed the cockroach allergen samples in her laboratory, she had

access to the repeated measurements database and this helped to guide our design effect due to clustering of apartments within buildings. The other papers did not have repeated measurements (thus the variance estimates were rather wide) and they also had more restrictive groups (e.g., nonsmoking pregnant women, Finnish families living in newly-constructed apartments) than is planned in the Green Housing Study. Thus, we believe that our conservative estimate to recruit residents in 64 apartments in each of 13 cities (total n= 832 homes) to account for potential loss-to-follow-up, should ensure adequate sample size for assessing differences in exposure levels.

Sample size for assessing asthma outcomes: The calculation for assessing differences in health markers were based upon a multi-site asthma intervention study (Morgan et al. 2004). In this study, 407 asthmatic children with the multi-factorial intervention (asthma trigger education, mattress covers, IPM, HEPA filter units) had fewer days (2.62 days ± 0.12) than those (n=414) without the intervention (3.21 days ± 0.13). Table 10 shows sample sizes with different assumptions of effect sizes using equation 2.

Equation 2. Sample size for asthma morbidity outcomes.

$$m = D * [2(z_{\alpha} + z_{\beta})^2 \{1 + (n - 1)\rho\}] / (n\Delta^2)$$

m = number in each group (e.g., intervention and non-intervention)

n = 1 (note: for differences of differences, we assumed a value of 1)

z_{α} = Z score for alpha = 0.05

z_{β} = Power, set at 0.80

ρ = correlation among repeated observations

Δ = d/ σ where d is the smallest meaningful difference and σ is the standard deviation

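### Equation 1 and Table 8 size a difference in average levels and count the pre-intervention baseline in n = 3, while the Overview announces change from each home's own baseline; for raw change scores Table 8 runs the wrong way with the correlation and overstates power below 0.5

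*Protocol*

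**What the plan says.** In the Protocol, Methods, Overview, changes in environmental measurements over the one-year follow-up are to be compared between green and control homes, so that "each home's follow-up measurements will be compared with its own baseline exposure level". The Overview adds that this two-group pre-post design "will increase ability to detect differences in exposure levels and asthma outcomes".

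Under Statistical Analysis and Related Issues, the exposure sample size comes from Equation 1, whose variance term is {1 + (n − 1)ρ}/n and in which "n = number of repeated measurements (equals 3 in this scenario". The list of assumptions taken from the New York pest-management study shows what the three measurements were: "3 repeated measures at: baseline (before IPM), 3months later (post-IPM), and 6months later (post-IPM". The correlation comes from the same list ("For the control homes, the correlations between baseline and 3-month follow-up cockroach allergen measurements", and those between 3 and 6 months, were about 0.5).

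The chosen 13 buildings per arm are the result at that value ("Assuming a correlation of 0.5 we get the following"). Table 8 varies the correlation from 0.2 to 0.8 and shows the required number of buildings rising throughout. On the test itself the text says only "We also assumed an alpha of 0.05 and a power of 80" percent, without naming one or two sides.

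For asthma outcomes, Equation 2 has the same form with "n = 1 (note: for differences of differences, we assumed a value of 1".

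**The concern.** The factor {1 + (n − 1)ρ}/n is the variance, relative to a single measurement, of the mean of n equally correlated measurements. It is right when the contrast is the group difference in that mean and every measurement carries the full difference d. A measurement taken before the intervention cannot carry d.

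The Overview describes a different contrast, in which baseline is subtracted. There a high correlation helps, because more of the home-to-home variation cancels, and a low correlation hurts. Table 8 says the opposite.

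The table is the protocol's only sensitivity analysis for the calculation that supports 13 buildings per arm. A reader planning for raw change scores would take from it that a correlation below 0.5 makes the study easier, when for that contrast it is where power is lost. The 0.5 was observed between visits three months apart and this study follows homes for 12 months, so the lower rows matter, although the protocol gives no value for the longer interval.

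**Working it through.** **Inputs (Protocol, Equation 1, Table 8 and the list of assumptions above them).** D = 3.62; Δ = 0.30; 25 apartments per building; alpha 0.05; power 0.80; n = 3; ρ = 0.5 adopted. Table 3 schedules three post-renovation visits: baseline part 2 (one week after the work, per Health and Environmental Assessments), 6 months and 12 months.

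**Step 1: reproduce Table 8.** Buildings per arm = D × 2(z_α + z_β)² × F / (Δ² × 25), with F = (1 + 2ρ)/3. With one-sided z values 1.645 and 0.842:

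- 3.62 × 2 × 2.487² / (0.09 × 25) = 19.89, so buildings = 19.89 × F.
- At ρ = 0.5, F = 0.667, giving 13.26 (printed 13).

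All 14 cells of Table 8 reproduce in this way. A two-sided 5% test gives 16.84 in this cell and does not reproduce.

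**Step 2: the factor for other contrasts.** With k post-renovation visits, equal correlation between all visits and the same SD at each:

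- mean follow-up minus baseline: F = (1 + (k − 1)ρ)/k + 1 − 2ρ, which is 1.5(1 − ρ) for k = 2 and (4/3)(1 − ρ) for k = 3;
- baseline-adjusted comparison: F = (1 + (k − 1)ρ)/k − ρ²;
- follow-up levels only: F = (1 + (k − 1)ρ)/k.

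**Step 3: buildings per arm (19.89 × F).**

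| ρ | Table 8 | Change, k = 2 | Change, k = 3 | Adjusted, k = 2 | Adjusted, k = 3 |
|---|---|---|---|---|---|
| 0.2 | 9 | 23.9 | 21.2 | 11.1 | 8.5 |
| 0.3 | 11 | 20.9 | 18.6 | 11.1 | 8.8 |
| 0.4 | 12 | 17.9 | 15.9 | 10.7 | 8.8 |
| 0.5 | 13 | 14.9 | 13.3 | 9.95 | 8.3 |
| 0.6 | 15 | 11.9 | 10.6 | 8.8 | 7.4 |
| 0.7 | 16 | 9.0 | 8.0 | 7.2 | 6.2 |
| 0.8 | 17 | 6.0 | 5.3 | 5.2 | 4.5 |

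Equation 1 and the change score need the same number where (1 + 2ρ)/3 = 1.5(1 − ρ), that is ρ = 3.5/6.5 = 0.538 for k = 2, and at ρ = 0.5 for k = 3.

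For follow-up levels only at ρ = 0.5, k = 2 gives F = 0.75 and again 14.9 buildings. With k = 3 the factor is Equation 1's own.

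**Step 4: power at 13 buildings (325 homes) per arm.** Power = Φ(0.30 × √(325/(2 × 3.62 × F)) − 1.645).

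| ρ | Equation 1 | Change, k = 2 | Change, k = 3 |
|---|---|---|---|
| 0.2 | 90.3% | 57.5% | 61.8% |
| 0.3 | 86.6% | 62.4% | 66.8% |
| 0.4 | 82.9% | 68.2% | 72.7% |
| 0.5 | 79.3% | 75.1% | 79.3% |
| 0.6 | 75.9% | 82.9% | 86.6% |

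With k = 2 and ρ = 0.5, 80% power is reached at Δ = 2.487 × √(2 × 3.62 × 0.75/325) = 0.32.

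Enrolling 832 and losing 20% leaves 332.8 homes per arm. With k = 2 the powers at ρ 0.5, 0.4 and 0.3 are then 75.9%, 69.1% and 63.3%, so the enrolment target changes little.

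**Step 5: Equation 2.** With n = 1 the bracket is 1 and ρ drops out, which is the two-sample formula for levels. A difference of differences with one pre and one post value has factor 2(1 − ρ), which equals 1 only at ρ = 0.5. The protocol gives no ρ for symptom-days. At 274 children per group, assumed values of 0.5, 0.4 and 0.3 give 80%, 73% and 68%.

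**The case against.** Four points can be made for the protocol.

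1. **The decision rests on the row for 0.5, and that row can be defended.** The study has three post-renovation visits. If all three carry the full effect, the change score needs 13.26 buildings, the same as Equation 1. A reader might infer that power is overstated at the adopted correlation, or that 13 buildings is simply wrong. The documents do not support that without a condition. The shortfall at 0.5 appears only if the visit one week after renovation does not carry the effect, and the source study measured its effect at 3 and 6 months. The protocol does not make this argument for n = 3 either: its three are the source study's, baseline included.

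2. **Change from baseline is not the only comparison described.** The sample size section speaks of an overall green-versus-control difference, Regression models puts primary interest in the green-versus-control coefficient, and the plan for Hypothesis 1 lists geometric means by rehabilitation type. For a comparison of levels, Table 8 runs the right way. This stands, and it limits the reversal to change scores. It does not rescue the count: with two effective follow-ups, levels alone also need 14.9 buildings at 0.5.

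3. **A baseline-adjusted analysis makes Table 8 safe over most of its range.** This also stands. At 0.5 it needs 9.95 or 8.3 buildings; only at 0.2 and 0.3 with k = 2 does it need slightly more than Equation 1 gives. One might infer that the own-baseline comparison gains power only above 0.5, so that the Overview is wrong. That is true of raw change scores alone, since adjustment gains at any correlation above zero.

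4. **D and the SD are carried over.** The protocol does not say whether 2.2 is the SD of a level or of a change, and 3.62 may be too large for changes if buildings differ persistently. A D of about 3.2 (3.62 × 0.667/0.75) would restore 13.26 buildings at ρ = 0.5 with k = 2. This is fair, and the figures are conditional on it.

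**Conclusion.** The arithmetic of Table 8 is sound; the mismatch is between the contrast it sizes and the one the Overview announces, together with an n that counts a pre-intervention measurement.

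For an unadjusted change score, Table 8's trend is reversed and power is overstated below ρ = 0.5: 68% to 73% against 83% at 0.4, and 62% to 67% against 87% at 0.3. At 0.5 the result depends on how many visits carry the effect: 79% with three, about 75% with two. Above about 0.54 Table 8 is conservative for the two-follow-up change score.

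All this assumes a one-sided 5% test, equal correlation at all visits, SD 2.2 for levels and D 3.62 for changes. The sidedness matters: two-sided, the 75% becomes about 64%, and Equation 1 itself would need 16.84 buildings, a larger shift at 0.5 than the change of contrast.

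On Equation 2 a reader might infer that 274 children per group is too few. The documents do not support that. No correlation is given for symptom-days, and at 0.5 the printed formula and the difference of differences agree. The point there is only that the assumption is unstated.

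**What to change.** - In Equation 1, do not count baseline in n. Let k be the number of post-renovation visits expected to carry the effect.
- Name the contrast that Equation 1 sizes and state whether the test is one- or two-sided.
- Reprint Table 8 for k = 2 and k = 3 with the matching factor: (1 + (k − 1)ρ)/k + 1 − 2ρ for a change score, or (1 + (k − 1)ρ)/k − ρ² for a baseline-adjusted comparison.
- Keep 832 homes and restate the claim. For a change score, one-sided, at 13 buildings and ρ = 0.5, that is about 75% (k = 2) to 79% (k = 3) power for 0.30 SD, or 80% for about 0.32 SD with k = 2.
- Preferably say in the Overview that the own-baseline comparison is baseline-adjusted, which supports the statement that it improves detection. If raw change scores are kept, say that for them the gain depends on ρ.
- Under Equation 2, say that n = 1 gives a two-sample formula for levels that equals a one-pre, one-post difference of differences at ρ = 0.5, and give the ρ assumed.

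The cost is recalculation and rewording, with no extra homes or visits. If raw change scores are kept, the stated exposure power or detectable effect may become slightly less favourable.

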1. To conduct an exposure assessment of chemical and biological contaminants, pesticides, volatile organic compounds (VOCs), fungi, indoor allergens (in terms of variety and concentration) in green vs. control housing.
 - a. We will measure interior levels of pesticides in surface wipe samples; fungi and indoor allergens in dust samples; and VOCs in air samples.
 - b. We will also compare biomarkers of VOCs and pesticides (in terms of variety and concentration) in the residents of green and control housing.
2. To examine the relationship between living in green vs. control housing and asthma morbidity (e.g, symptoms, ED visits, use of medications, lost school/work days) of children with doctor-diagnosed asthma (ages 7-12 years). We will adjust for allergic sensitization and ETS.
 - 2.1 To examine the relationship between living in green vs. control housing and respiratory morbidity of the mothers/primary caregivers of the enrolled children.

Figure 1. Hypothesized relationships among green housing rehabilitation strategies, environmental exposures, and asthma-related health outcomes.

Hypotheses

1. Green housing utilizes different strategies to reduce environmental contaminants. We hypothesize that these strategies will lead to 1) lower levels of environmental contaminants compared with those of control housing, and 2) lower levels of related biomarkers in the residents of green vs. control housing.
 - a. Integrated pest management (IPM) is a method to reduce pests such as cockroaches and mice by eliminating entry points in the home and harborage areas.
 - i. We hypothesize that IPM will result in lower cockroach and mouse allergen levels while at the same time lowering the concentrations and array of pesticides in the green vs. control homes.
 - ii. We hypothesize that concentrations of pesticide metabolites in sera of children living in green housing will be lower than those living in control homes.
 - b. The use of low VOC paints, carpeting, and other building materials should lead to lower concentrations of aldehydes, ketones, and alcohols.
 - i. We hypothesize that the levels of VOCs will be lower at baseline in green-renovated vs. control homes.
 - ii. We hypothesize that concentrations of VOCs in urine of children with asthma (ages 7-12 years) living in green housing will be lower than those living in control homes.

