Figure 3. Comparison of dust mite allergens in green vs. traditional buildings.

Dust mite allergen concentrations were low in both green and traditional apartments which may account for inability to detect significant differences. In addition, cockroach and mouse allergens were also rarely detected, 2/65 (3%) and 9/65 (14%), respectively. Again, we were not able to detect a significant difference between green and traditional housing with

these rarely detected allergens. Given that both housing complexes were comprised of elderly residents, these findings will not likely be generalizable to housing with children.

[figure not shown]

Figure 4. Comparison of pesticides in green vs. traditional buildings.

Pesticide levels were much higher than those reported in a Boston Study (Julien et al., 2008). Nonetheless, we were not able to detect a difference between the two types of housing. We speculate that resident use of pesticides was a factor that could have

overwhelmed any difference due to building-wide pesticide application practices. In addition, generalizability to other regions of the country could be a factor due to different pesticide application habits and availability.

Based upon preliminary formaldehyde data (n=26 traditional units and n= 24 green units), formaldehyde levels were significantly higher in the green units (0.02 ppm vs. 0.05 ppm). However, no adjustment for ETS exposure or open windows has been conducted. With this small sample size, adjustments might not reach statistical significance, but could help in understand source contributions.

IV. METHODS

Overview

The United States Department of Housing and Urban Development (HUD) subsidizes both publicly- and privately-owned housing across the country, notably in urban areas. HUD requires that these subsidized properties be rehabilitated to maintain a certain level of habitability. CDC will leverage the opportunity to study rehabilitated properties in thirteen (13) study locations (large metropolitan areas that are located in different climactic regions of the United States). The selection criteria are described below:

1. City must have one or more housing developments which are receiving a HUD-subsidized green-renovation.

[figure not shown]
- a. These renovations must occur within the timeline of our study period (5 years, although, we will ask OMB for a continuation prior to the expiration of the initial 3-year OMB approval)

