D = Design effect due to clustering (This was not in the formula used by Diggle et al. 1994, but was added to adjust for clustering expected in our study). Based upon the Kwon et al paper (2003) that showed a design effect of 1.5 was helpful for designing cluster studies to assess asthma outcomes in national surveys (e.g., BRFSS and NHANES), we assumed a slightly smaller design effect equal 1.2 due to the expected low number of expected of average children per cluster).

Summary of sample size for asthma outcomes: Based upon both the Morgan et al. (2004) and Krieger et al (2005) studies, a sample size of at least n=274 in each group (Green intervention vs. non-intervention) should provide 80% power to detect differences in asthma outcomes such as symptom-days and urgent care visits. As mentioned in the summary above, we will enroll the children from 832 homes in order to ensure adequate power to detect both the asthma and exposure outcomes.

Main Variable Definitions

Type of rehabilitation: The main variable of interest is the type of home (green vs. control); however, within each type, there are different permutations. For example, HUD has two levels of green which are based upon the acceptance of HUD-approved recommendations: Level 1) landlord agrees to implement at least 75% of the dollar amount of green repairs and improvements; and Level 2) landlord agrees to implement at least 50% of the dollar amount. While discretizing the green rehabilitation into Level 1 and Level 2 categories could simplify our analysis, we acknowledge that the two different levels do not necessarily capture green materials or practices that are potentially related to health. For example, a green home could have low VOC paint, or low VOC carpet, or replace the kitchen cabinets with low VOC materials, or have some combination of these activities. A control home may also include some green materials (such as low flow toilets or EnergyStar appliances)—the distinction here is that a control home is not required to use green materials or practices. Therefore, we will attempt to isolate the main effects of specific background variables such as low VOC paint, low VOC carpet, and kitchen cabinet replacement.

Allergens in the homes: Variables related to dust mite (Der p 1 and Der f 1), cockroach (Bla g 2), cat (Fel d 1), and mouse (Mus m 1) allergen in the homes may take the form of continuous measures of specific allergens or

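### The figures that set enrolment rest on an undeclared one-sided 5% test; at two-sided 5% the 832 homes, after 20% loss, give about 70% power for cockroach allergen at Δ 0.30 and 78% for symptom-days

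*Protocol*

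**What the plan says.** All of this is in Protocol Section IV, Statistical Analysis and Related Issues.

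- **Error rates.** The text under Equation 1 reads "We also assumed an alpha of 0.05 and a power of 80"%. The symbols are defined only as "Z score for alpha = 0.05" and "Power, set at 0.80". The footnote to Table 9 repeats 0.05 and 0.80. Neither one-sided nor two-sided appears anywhere.
- **Exposures.** The overview concludes "we estimate that we will need at least 13 green buildings and 13 control buildings with at least 25 apartments in each building", 650 in total. This is the Table 8 cell for Δ 0.30 and correlation 0.5.
- **Asthma.** The summary after Equation 3 says "a sample size of at least n=274 in each group (Green intervention vs. non-intervention) should provide 80% power to detect differences in asthma outcomes". The 274 is the Table 10 entry for Δ 0.232, and the 0.20 row prints 274 as well.
- **Enrolment.** 832 homes, 416 per arm, with 20% loss expected over the year. The overview says this secures adequate power for both kinds of outcome.
- **Direction.** Hypothesis 1 (Section I) expects "lower levels of environmental contaminants compared with those of control housing". Section III reports from the pilot that "formaldehyde levels were significantly higher in the green units (0.02 ppm vs. 0.05 ppm").

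**The concern.** An alpha of 0.05 with no qualifier is usually read as two-sided. If the printed sizes came from a one-sided calculation, a reader who takes alpha and power at face value will believe the trial has more power than it has. The protocol makes a specific claim (80% power, 832 homes sufficient for exposure and asthma), so the gap lies in its own numbers and not in a detail left for later. At stake is how a null result would be read for the smaller exposure effects, which are the ones that set the number of buildings.

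**Working it through.** **Inputs, all from the protocol.** Equations 1 and 2: m = D·2(z_α + z_power)²·{1 + (n−1)ρ}/(nΔ²) per arm.
- Table 8: D = 3.62, n = 3, 25 apartments per building.
- Table 9: D = 3.6. The equation is not named there; n = 1 reproduces the entries.
- Table 10: D = 1.2, n = 1.

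At 80% power, 2(1.645 + 0.842)² = 12.365 one-sided and 2(1.960 + 0.842)² = 15.698 two-sided.

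**Step 1: reproduce the printed figures, one-sided.**

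Table 8, Δ 0.30, ρ = 0.5: 3.62 × 12.365 × 2/(3 × 0.09) = 331.6 homes; divided by 25 this is 13.26 buildings (printed 13). Over ρ = 0.2 to 0.8:
- Δ 0.30: 9.28, 10.61, 11.94, 13.26, 14.59, 15.92, 17.24 (printed 9, 11, 12, 13, 15, 16, 17).
- Δ 0.377: 5.88, 6.72, 7.56, 8.40, 9.24, 10.08, 10.92 (printed 6, 7, 8, 8, 9, 10, 11).

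All 14 cells match to the nearest building. Two-sided, none does.

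| Figure | Printed | One-sided | Two-sided |
|---|---|---|---|
| Table 8, Δ 0.30, ρ 0.5 (buildings) | 13 | 13.26 | 16.84 |
| Table 9, formaldehyde Δ 0.33 | 408 | 408.8 | 519 |
| Table 9, formaldehyde Δ 0.77 | 75 | 75.1 | 95 |
| Table 9, formaldehyde Δ 1.10 | 37 | 36.8 | 47 |
| Table 9, piperonyl butoxide | 418 | 409 to 418 | 519 to 531 |
| Table 10, Δ 0.232 | 274 | 274 to 276 | 348 to 350 |

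For piperonyl butoxide, the quoted means and standard errors (25 homes) give SDs of 3.55 and 1.10, pooled 2.628, so Δ = 0.86/2.628 = 0.327. With D = 3.62 that is 418.0 one-sided. For symptom-days, reading the ± values as standard errors gives SDs of 2.42 and 2.65, pooled 2.535, so Δ = 0.59/2.535 = 0.2327 and m = 274.0 one-sided.

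**Step 2: the other rows of Table 10.**

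| Δ | Printed | One-sided, D 1.2 | Two-sided, D 1.2 | One-sided, D 1.5 |
|---|---|---|---|---|
| 0.20 | 274 | 371 | 471 | 464 |
| 0.30 | 206 | 165 | 209 | 206 |
| 0.35 | 151 | 121 | 154 | 151 |
| 0.40 | 116 | 93 | 118 | 116 |

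The 0.20 row fits nothing and repeats the 274. The last three rows fit one-sided only at D = 1.5, which is not the value the protocol adopts; two-sided at D = 1.2 they are within 3%.

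**Step 3: what two-sided 5% would need.** Cockroach allergen at Δ 0.30: 3.62 × 15.698 × 2/0.27 = 421 homes per arm, 17 buildings. With 20% loss, 2 × 420.9/0.8 ≈ 1,053 homes. Symptom-days: 348 to 350 children per arm, or 870 to 875 enrolled.

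**Step 4: two-sided power of the enrolled sample.** After loss, 416 × 0.8 = 332.8 per arm. Power = Φ(√[m·n·Δ²/(2D{1 + (n−1)ρ})] − 1.96).
- Cockroach allergen, Δ 0.30: √(332.8 × 0.27/14.48) = 2.491, giving 70.2% (79.5% with no loss).
- Cockroach allergen, Δ 0.37: 86.7%.
- Δ 0.33 analytes: √(332.8 × 0.1089/7.2) = 2.244, giving 61.2% (70.8% with no loss).
- Symptom-days, Δ 0.232: √(332.8 × 0.0538/2.4) = 2.732, giving 78.0% (86.3% with no loss). At exactly 274 per arm, 69.8%.
- Formaldehyde at 0.77 and 1.10 needs 95 and 47 per arm, well within 333.

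**Step 5: adjusting for the pre-renovation value.** With three post-renovation visits and ρ = 0.5 between every pair, the variance factor falls from (1 + 2ρ)/3 = 0.667 to 0.667 − ρ² = 0.417. Cockroach allergen at Δ 0.30: √(332.8 × 0.09/(2 × 3.62 × 0.417)) = 3.15, giving about 88% two-sided.

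**The case against.** **A one-sided test may have been intended.** Every hypothesis is directional, and the z definition read literally gives 1.645. That stands: a reader might infer that a one-sided test is indefensible here, and the protocol does not support so strong a claim. The contrary formaldehyde result comes from 26 and 24 units in one region, housing elderly residents, without adjustment for tobacco smoke or open windows, and formaldehyde does not set the 832. But one-sided testing is never declared, and the pilot is reason enough to ask for a justification.

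**An adverse effect would still be visible.** One might infer that the trial could not report harm. The plan is largely estimation (geometric means, odds ratios, rate ratios), which would show either direction. How the tests will be run may be settled in a SAP that was not available. What remains is that the printed sizes and the power claim are in the protocol.

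**The shortfall is uneven.** It would be wrong to say that the trial lacks 80% power throughout, or that all of Tables 8 to 10 reproduces one-sided; Steps 2 and 4 show otherwise. Nor is the Δ 0.33 gap due to sidedness alone: with 333 per arm the one-sided power is only 72.5%, because Table 9 asks for 408 to 418.

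**Another reading fits.** Two-sided 5% with 70% power gives almost the same sizes (13.2 buildings, 275 children, 408 homes), but it contradicts the 80% stated throughout.

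**Conclusion.** Wrong as written, and material mainly for the smaller exposure effects. At the stated 80% power, the entries that fix enrolment imply an undeclared one-sided 5% test. Under a two-sided reading, with all other inputs as the protocol gives them and 20% loss, power falls about 10 points short for cockroach allergen at Δ 0.30, about 19 points short for the Δ 0.33 analytes and about 2 points short for symptom-days. Table 10 needs correcting under either reading.

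The 88% adjusted figure assumes that the 0.5 correlation, observed between successive visits in control homes of the pest-management study, holds for all pairs of visits here, and that the design effect does not change. For symptom-days the protocol gives no baseline correlation. The same adjustment would give about 80% to 89% for ρ from 0.2 to 0.5, and only if the effect size is not already a change score. The note to Equation 2, which ties n = 1 to differences of differences, leaves that open, so no adjusted figure for symptom-days can be relied on.

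**What to change.** 1. State the test as two-sided 5%. If one-sided is intended, declare it and justify it against the hypotheses and the pilot formaldehyde result.
2. Recompute Tables 8 to 10 on that basis, with one stated design effect for each outcome. In Table 10, correct the 0.20 row and reconcile the 0.30 to 0.40 rows with the stated 1.2.
3. Restate the power of the fixed 832 homes after 20% loss, by outcome and effect size, in place of the general assurance of adequacy.
4. Specify the home's pre-renovation value as a covariate in the exposure comparison. This fits the design, which already compares each home with its own baseline. Give the resulting power with its assumed correlation.
5. For symptom-days, say whether the effect size is a change score, and show any baseline-adjusted power as a range over assumed correlations.

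The cost is a rewritten sample-size section and a less favourable stated power for the unadjusted analysis. No homes, visits or measurements are added.
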